# **I、 Research Background**

Colonoscopy is a must-have item in colorectal cancer check-ups, and for high-risk groups, annual check-ups are the most effective way of early prevention; A large amount of polyethylene glycol (PEG2000-4000) is used as a laxative and lubricant in colonoscopy at present; The extensive use of PEG can cause long-term and irreversible damage to the gut microbiota, posing a great threat to health.

The appendix, located at the base of the cecum, is a slender tubular structure that protrudes from the posterior wall inside the cecum and was once thought to be part of an evolutionary redundancy. Appendicitis has long been the most common surgical acute abdominal disease, and once acute appendicitis occurs, traditional treatments often opt for the removal of the appendix. In recent years, researchers have revealed that appendectomy is associated with mental disorders, colorectal cancer, cardiovascular diseases, etc. Besides being an important organ involved in immunity, the appendix also has the function of storing and protecting intestinal microbiota. When there is a disruption of the gut microbiota in the human body, the microorganisms retained in the appendix are released into the gut to reduce the impact of the disruption. Previous researchers' metagenomic sequencing of gut microbiota in patients who have undergone appendectomy shows significant changes in their gut microbiota compared to the normal population, which in turn affects central nervous system function through the microbiota-gut-brain axis and poses potential risks to host health and behavior, such as Parkinson's disease. Therefore, appendectomy may have potential adverse effects on the human body, such as significantly altering the composition of the gut microbiota, reducing the ability to restore intestinal homeostasis, and lowering the production of short-chain fatty acids (SCFAs).

This study will observe the effects of PEG on the gut microbiota, and by analyzing the changes in the gut microecology before and after colonoscopy, design better intestinal cleansing drugs and intestinal repair probiotics to further reduce the adverse effects of colonoscopy on patients. At the same time, explore the interaction between the appendix and the gut microbiota and its significance.

## **2. Objectives of the study**

The study intends to recruit a group of people who have undergone appendectomy for colonoscopy, (1) to observe changes in gut microbiota before and after colonoscopy in the appendectomy population; (2) To analyze whether the changes in gut microbiota before and after colonoscopy in the appendectomy population were different from the recovery of the normal population.

### **Iii. Study Design**

This study uses a parallel controlled monitoring clinical trial approach to investigate the short-term and long-term effects of PEG use on the gut microbiota of patients, including tracking analysis of the recovery and impairment of the gut microbiota, and comparing the recovery and impairment of the microbiota with those who did not undergo appendectomy to design corresponding microecological restoration probiotics. This study used bioinformatics methods to statistically analyze the data information of the samples.

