### **2. Exclusion criteria**

Subjects excluded the following conditions: (1) contraindications for colonoscopy: such as cardiopulmonary insufficiency, etc. (2) Intolerance to PEG laxatives; (3) Pregnant women; (4) Mental disorders. Among them, the colonoscopy population without appendectomy was used as the control; 4) Use of antibiotics within half a year.

Control subjects excluded the following conditions: (1) presence of organic disease; Such as cardiopulmonary insufficiency, etc. (2) Pregnant women; (3) Mental disorders; 4) Use of antibiotics

[figure not shown]
within half a year.

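### The Study Design section states its aim as the effect of PEG, but the groups differ by appendectomy, so a PEG-specific effect cannot be identified

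*Protocol*

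**What the plan says.** The Protocol states its target in two ways.

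- **As an effect of PEG.** Section Iii (Study Design) says the parallel controlled approach is used "to investigate the short-term and long-term effects of PEG use on the gut microbiota of patients". The last paragraph of the Research Background says "This study will observe the effects of PEG on the gut microbiota". It would read this effect "by analyzing the changes in the gut microecology before and after colonoscopy", and hopes to use the result to "design better intestinal cleansing drugs and intestinal repair probiotics".
- **As change around colonoscopy.** Section 2 (Objectives of the study) sets out first "to observe changes in gut microbiota before and after colonoscopy in the appendectomy population", and second to ask whether those changes "were different from the recovery of the normal population". PEG is not named in either objective.

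The comparison group is defined by appendectomy. Study Design speaks of "comparing the recovery and impairment of the microbiota with those who did not undergo appendectomy", and the exclusion criteria in section 4 say that "the colonoscopy population without appendectomy was used as the control". The inclusion criteria require planned colonoscopy of the subjects but not of the controls. PEG intolerance is an exclusion for the subjects only.

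**The concern.** An effect of PEG is a causal statement about one agent. To support it, some comparison must let PEG vary while time and the procedure do not. The control group here serves a different question, namely whether recovery depends on the appendix. Because Study Design calls the approach controlled in the same sentence that names PEG, a reader could take the control to be a control for PEG.

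What is at stake is the conclusion. Followed as written, the plan would report a before/after change as a PEG effect, when the change belongs to PEG, the procedure and elapsed time together. The Research Background would then carry that reading into the design of cleansing drugs. No later analysis choice can repair this, because an analysis cannot recover a contrast that the design does not contain.

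**Working it through.** The plan gives no figure to reproduce on this point. The question is which effects the described design can separate.

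**Inputs.** There are two groups (a = 1 for appendectomy, 0 for control; Study Design and section 4) and two periods (t = 0 before colonoscopy, 1 after; Objectives). That gives four cells. PEG exposure depends on how the control definition is read:

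| Cell (a, t) | Reading A: controls also receive PEG | Reading B: controls are PEG-free |
|---|---|---|
| (0, 0) | 0 | 0 |
| (0, 1) | 1 | 0 |
| (1, 0) | 0 | 0 |
| (1, 1) | 1 | 1 |

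Reading A follows the description of the controls in the exclusion criteria. It also fits the word recovery in the Objectives, which presupposes that controls were perturbed. Reading B is possible only because the control inclusion criteria do not ask for colonoscopy.

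**Model.** Cell mean = b0 + bA·a + bT·t + bG·PEG, where bT carries everything that changes with period other than PEG.

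**Reading A.** PEG equals t in every cell, so two columns are identical and the rank is 3 of 4.
- Change in controls: bT + bG.
- Change in the appendectomy group: bT + bG.
- Only the sum can be estimated. With an appendectomy-by-period term bAT added, the rank is 4 of 5. The difference between the two changes is then bAT, which is the second objective, but bG is still tied to bT.

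**Reading B.** PEG equals a·t, and the rank is 4 of 4.
- Change in controls: bT. Change in the appendectomy group: bT + bG. The difference is bG.
- This holds only if appendectomy does not alter the time course, which is the very thing the second objective asks. With bAT added, the rank is 4 of 5 and the difference is bAT + bG.
- With a separate term bC for the colonoscopy, which occurs in the same cell as PEG, the rank is again 4 of 5 and the difference is bC + bG.

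**Later samples.** Follow-up visits do not change this. Each one comes after both PEG and the procedure, so a long-term PEG effect is no better separated from the procedure than a short-term one.

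Under neither reading is bG isolated. Under Reading A, both formal objectives can be estimated without it.

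**The case against.** The strongest reply is that the formal objectives are sound. They ask for change around colonoscopy and for its difference by appendectomy status. Neither needs a PEG-free group, and period effects common to both groups cancel in the second. No PEG-specific hypothesis or test is written down, and the Research Background says only that effects will be observed. All of that stands, and it is why the severity is minor. It does not remove the point, because Study Design is where the Protocol says what its approach investigates, and that section names PEG.

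A second reply is that the controls may not receive PEG at all. The text leaves this open, so a flat statement that no PEG-free comparator exists would go too far. The working shows that the conclusion does not depend on it.

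A reader might also infer several stronger things that the documents do not support:

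- **That the study plans to choose between cleansing agents.** Only one agent is named. Cleansing drugs appear only in the Research Background, as an aspiration. Study Design speaks of restoration probiotics.
- **That ordinary within-person fluctuation is unmeasured for want of a repeat baseline.** The technical route in section Vi is a figure that is not shown, so the sampling schedule cannot be judged.
- **That distance from baseline is a flawed endpoint.** Section VIII uses Bray-Curtis distance only for principal coordinate analysis.
- **That diet change is part of the preparation.** The Protocol does not say so, and time and the procedure are enough for the argument.

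**Conclusion.** Wrong as written, severity minor. The aim in Study Design and at the end of the Research Background is one that the described design cannot deliver. A PEG-specific effect is aliased with period and procedure if controls receive PEG, and with appendectomy-by-period and procedure if they do not. The share of any observed change that is due to PEG cannot be estimated, so no numerical size is offered.

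The conclusion rests on the groups being defined by appendectomy status alone, as section 4 and Study Design state, and on no other section describing a group with a different preparation or with sampling over time without preparation. It does not rest on the sample size of about 10, and it does not touch the two formal objectives. A reader should not infer that the trial fails its objectives or that it needs a PEG-free arm to meet them.

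**What to change.** 1. In Study Design and the last paragraph of the Research Background, restate the aim to match the Objectives: change in gut microbiota after bowel preparation and colonoscopy, and its difference by appendectomy status.
2. Draw no causal conclusion specific to PEG from the before/after change.
3. In the Research Background, do not present the results as a basis for designing cleansing drugs.
4. Reconcile the inclusion and exclusion criteria in section 4 on whether controls undergo colonoscopy with PEG. The second objective is read differently in the two cases, so the text should settle which applies.

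Items 1 to 3 are wording only. They cost nothing and leave the groups, objectives and analyses as they are. Item 4 is a clarification of text that recruitment needs in any case.

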Additionally, calculate the Bray-Curtis distance using the vegan package for principal coordinate analysis (PCoA). Linear discriminant analysis effect size (LEfSe) analysis was used for the Kruskal-Wallis test and the Wilcoxon rank sum test, and a  $p < 0.05$  was considered statistically significant. The LDA score was set to 2.0 to identify the characteristics with significant differences between groups. This study retained taxa with an average relative abundance greater than 0.0001(0.01%). The bar charts were visualized using the "ggplot2" package in R software (version 4.0.5)(<https://www.r-project.org/>).

All data were expressed as mean  $\pm$  standard error (SEM). The differences between groups were analyzed by one-way ANOVA using GraphPad Prism 7.0 software, and the results of the analysis were obtained by Tukey Test.

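### The protocol can be read as drawing the restoration probiotic from two different contrasts, and the tests it names suit neither reading of the PEG (polyethylene glycol) effect

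*Protocol*

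**What the plan says.** The Research Background (section I) gives one source for the product: "by analyzing the changes in the gut microecology before and after colonoscopy, design better intestinal cleansing drugs and intestinal repair probiotics". It then adds the appendix question as a parallel aim: "At the same time, explore the interaction between the appendix and the gut microbiota and its significance".

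The Study Design (section III) sets out to "investigate the short-term and long-term effects of PEG use on the gut microbiota of patients". It lists two components in one sentence. The first is "including tracking analysis of the recovery and impairment of the gut microbiota". The second is "comparing the recovery and impairment of the microbiota with those who did not undergo appendectomy to design corresponding microecological restoration probiotics".

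The Objectives (section 2) are, first, "to observe changes in gut microbiota before and after colonoscopy in the appendectomy population", and second, whether those changes "were different from the recovery of the normal population". Neither objective mentions a probiotic.

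The statistical section (VIII) names LEfSe with the Kruskal-Wallis and Wilcoxon rank sum tests at p < 0.05, and one-way ANOVA with Tukey's test. On LEfSe it says: "The LDA score was set to 2.0 to identify the characteristics with significant differences between groups". It does not say whether the groups are the two arms, the sampling times, or both.

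**The concern.** The two contrasts answer different questions. Change within a person shows what bowel preparation with PEG removes and what returns. The comparison of appendectomy patients with people who kept their appendix shows whether that loss or recovery depends on the appendix. Anything PEG does equally to both arms drops out of the second contrast.

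A repair product meant to offset the harm of colonoscopy would normally rest on the first contrast. Taken literally, the purpose clause at the end of the Study Design sentence rests it on the second. If that reading were followed, taxa lost by everyone would enter the candidate list only by chance, and the information on PEG that all participants carry would not drive the choice.

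**Working it through.** **Inputs from the protocol.** About 10 people, with no split between arms (section 5); significance at p < 0.05 (section VIII). The protocol gives no effect size, SD or power, so there is no stated figure to reproduce.

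**Inputs assumed.** 5 people per arm; a ten-fold drop (1 log10) after PEG; an SD of within-person change of 0.5 to 1.4 log10; two-sided testing; one taxon, no multiplicity adjustment.

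**1. The arms as groups, both taking PEG.** Let PEG change a taxon by −d in each arm. The between-arm contrast of change is (−d) − (−d) = 0 for every d. The within-person contrast is −d. The between-arm test therefore rejects only at its false-positive rate:

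- Asymptotic rank test, 5 versus 5, by full enumeration: 14 of 252 arrangements reject, 14/252 = 5.6%. Simulation gives 5.5%.
- Simulation with d = 1, 1.5 and 2 SD: t test 4.5% to 5.4%; exact rank test 2% to 4%.

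**2. Within-person change.** Power of the paired t test comes from the noncentral t distribution with n − 1 degrees of freedom and noncentrality √n × (1/SD). At SD 0.7 this is √10/0.7 = 4.52 for n = 10 and √5/0.7 = 3.19 for n = 5.

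| SD of change (log10) | Appendectomy arm only, n = 5 | Both arms, n = 10 |
|---|---|---|
| 0.5 | 0.909 | 1.000 |
| 0.7 | 0.671 | 0.979 |
| 1.0 | 0.401 | 0.803 |
| 1.4 | 0.235 | 0.522 |

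A paired rank test on 10 people gives nearly the same result (0.97 at SD 0.7). On 5 people, the exact two-sided signed-rank test cannot reach 0.05, because its smallest p-value is 2/32 = 0.0625.

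**3. Time points as groups, with an independent-sample test.** Assume also a person-to-person SD of 1.0 log10. An SD of change of 0.7 means a within-person variance of 0.7²/2 = 0.245 per sample. The unpaired test sets the drop against a variance of 2 × (1.0 + 0.245) = 2.49; the paired test uses 0.7² = 0.49. The unpaired variance is 2.49/0.49 ≈ 5 times as large. In simulation with 10 people, detection falls from about 98% to about 49%.

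**4. Controls not taking PEG.** The contrast becomes −d − 0 = −d, so the PEG effect is visible. The normal-approximation power at 5 per arm is 0.35, 0.66 and 0.89 for d = 1, 1.5 and 2 SD. But the arms then differ in both PEG and appendectomy, so the two effects cannot be separated.

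**The case against.** The case against a stronger reading is good, and most of it stands.

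- **The Study Design sentence is ambiguous.** Its purpose clause follows the comparison directly, but can also govern the tracking analysis listed just before it. Read that way, it agrees with the Background. So the documents do not establish that the product will come from the wrong contrast, only that they can be read so.
- **A reader might infer that the Background requires the probiotic to repair taxa depleted equally in both arms.** It does not say this. It speaks of before-after change and of reducing the adverse effects of colonoscopy. Shared losses are part of that change, not all of it.
- **A reader might infer that LEfSe selects the probiotic's taxa.** The statistical section makes no such link and does not define its groups. Tukey's test, a multiple-comparison procedure, would fit groups that include sampling times.
- **The probiotic is not a listed objective**, and objective 1 is already a before-after aim, though for appendectomy patients only.
- **The cancellation needs PEG-exposed controls.** The exclusion criteria describe the controls as a colonoscopy population, and comparing recovery presupposes exposure. The control inclusion criteria, however, do not require colonoscopy.
- **A separate SAP may specify a paired analysis.** Its absence from the protocol is not the complaint. The point is that the protocol ties one product to two contrasts and that every test it does name ignores pairing.

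On magnitude, the 98% is for one taxon at unadjusted 0.05. Metagenomic data hold many taxa, so it flatters the paired analysis.

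**Conclusion.** The concern holds as a point of reconciliation. The Background and the Study Design can be read as tying the probiotic to different contrasts, and the named tests settle the matter badly under either meaning of groups. With arms as groups and PEG in both, shared losses are invisible. This follows from the algebra and holds whatever the size of the PEG effect. With time points as groups, the effect is visible but pairing is thrown away.

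The other figures (98% pooled and paired, 67% in the appendectomy arm alone, about 49% unpaired, all at SD 0.7) are illustrations on assumed values. Over SDs of 0.5 to 1.4 log10, pooled paired power runs from over 99% down to 52%, against roughly 5% for the between-arm contrast. None of this shows that the investigators will choose the wrong taxa; it shows that the text permits it and that a better analysis needs no new samples.

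**What to change.** Reword the Study Design sentence to match the Background: candidate taxa for PEG repair come from within-person change, from before to after colonoscopy and on to follow-up. In the statistical section, name a paired or mixed model for that change, fitted over all PEG-exposed participants with group as a factor, and show the appendectomy arm separately as well, since objective 1 concerns that arm. Keep the between-arm difference in change for objective 2 and for marking taxa whose loss or return depends on the appendix. Define what the groups are in each named test, and reconcile the control inclusion criteria with the description of the controls as a colonoscopy population, since the pooled analysis depends on who took PEG.

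The cost is a few sentences, with the same samples. The one downside is that the pooled list describes the average of the two arms, which is why the separate display is needed.

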## **4. Selection of subjects**

### **1. Inclusion criteria**

The subjects were mainly recruited who met the following conditions: 1) Had undergone appendectomy or appendectomy for right-sided colon cancer; 2) were aged between 18 and 75 years old. 3) Prepare for colonoscopy; 4) Be in good health and have no history of major organ disease.

Control subjects were recruited to meet the following conditions: 1) age 18-75 years; 2) No appendectomy or right colon cancer appendectomy; 3) Good health, no history of major organ disease.

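### The control eligibility lists do not require colonoscopy or PEG preparation, although another sentence defines the controls as colonoscopy patients; to the extent that unprepared controls enrol, the appendix comparison is confounded with PEG exposure

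*Protocol*

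**What the plan says.** All references are to the Protocol.

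- **Inclusion criteria, appendectomy group.** The list includes "3) Prepare for colonoscopy".
- **Inclusion criteria, controls.** The whole list is "1) age 18-75 years; 2) No appendectomy or right colon cancer appendectomy; 3) Good health, no history of major organ disease". Neither colonoscopy nor PEG appears in it.
- **Exclusion criteria, first list.** It names "1) contraindications for colonoscopy: such as cardiopulmonary insufficiency, etc" and "2) Intolerance to PEG laxatives", then pregnancy and mental disorders. Next comes a sentence about the control group: "Among them, the colonoscopy population without appendectomy was used as the control". The list closes with recent antibiotic use.
- **Exclusion criteria, controls.** The list covers organic disease (with cardiopulmonary insufficiency as the example), pregnancy, mental disorders and recent antibiotic use. PEG intolerance is absent.
- **Objectives of the study, item 2.** It asks whether the changes around colonoscopy in the appendectomy group "were different from the recovery of the normal population".
- **Study Design.** The aim is the effect of PEG on the microbiota, with recovery and impairment compared against people who have not had an appendectomy.
- **Estimation of sample size.** About 10 people, with no split between groups.

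**The concern.** The Protocol defines its controls in two ways that do not agree. A healthy 40-year-old with an appendix and no planned colonoscopy meets every item on the control inclusion list and can pass the control exclusion list. The same person falls outside the definition of controls given in the middle of the first exclusion list. Staff recruiting from the lists could enrol someone whom that sentence rules out.

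The difference matters because the study compares responses to a perturbation. Every appendectomy subject is preparing for colonoscopy. A control who is not prepared has nothing to recover from, so such a person's change over time says nothing about how an intact appendix affects recovery. If unprepared people enter the control group, the difference in change between groups mixes the effect of having no appendix with the effect of the bowel preparation. This is settled at enrolment, so a later analysis plan can mitigate it only in part.

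**Working it through.** **Step 1. Eligibility side by side.**

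| Item | Appendectomy group | Controls |
|---|---|---|
| Preparing for colonoscopy | required | not in the list; implied by the sentence in the first exclusion list |
| Contraindication to colonoscopy | excluded; example cardiopulmonary insufficiency | not named as such; the same example is excluded under organic disease |
| PEG intolerance | excluded | absent |
| Pregnancy, mental disorders, antibiotics in the past half year | excluded | excluded |

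The clear gaps for controls are the colonoscopy requirement and PEG intolerance. The contraindication gap is only partial, because the one example given is excluded in both groups.

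**Step 2. Size of the bias in general.** Let m be the mean change in an unprepared person, P the shift in that change from preparation in someone with an appendix, A the further shift in a prepared person without an appendix (the target of objective 2), and f the fraction of controls who are not prepared.

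- Appendectomy group, mean change: m + P + A
- Controls, mean change: m + (1 − f)P
- Difference: A + fP

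The bias is f × P. The Protocol gives neither f nor P.

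**Step 3. Range over f.** The Protocol states only the total, about 10, and does not say whether controls are counted in it. Assume 5 per group.

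| Controls prepared | f | Expected difference |
|---|---|---|
| 0 of 5 | 1.0 | A + 1.0P |
| 1 of 5 | 0.8 | A + 0.8P |
| 2 of 5 | 0.6 | A + 0.6P |
| 3 of 5 | 0.4 | A + 0.4P |
| 4 of 5 | 0.2 | A + 0.2P |
| 5 of 5 | 0 | A |

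With 0 of 5 prepared, the appendectomy and PEG indicators are identical (correlation 1.0). A model with an intercept, A and P then has rank 2 for 3 parameters, so A and P cannot be separated. With 1 to 4 prepared the rank is 3, so separation is possible if exposure is recorded. With 5 of 5, PEG is constant and the group difference estimates A alone.

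**Step 4. What the worst case would do to a test.** Take f = 1, A = 0, 5 per group and a two-sided 0.05 test on the change (8 degrees of freedom; with two groups, one-way ANOVA is the same test). The noncentrality is P / √(2/5), with P in SDs of the change. The values of P are assumed.

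| Assumed P (SD) | Probability of a significant difference |
|---|---|
| 0 | 5% |
| 0.5 | 11% |
| 1.0 | 29% |
| 1.5 | 55% |
| 2.0 | 79% |

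**Step 5. What restriction to prepared controls would cost.** Suppose 3 of 5 controls are prepared and only they are used. The standard error of the difference is proportional to √(1/5 + 1/3) = 0.730, against √(1/5 + 1/5) = 0.632 with all five. It is 0.730 / 0.632 = 1.15 times as large. The bias is removed, with a loss of precision in a study that is already very small.

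**The case against.** The strongest reply is that the Protocol already shows its intent. The sentence in the first exclusion list says the controls have colonoscopy. Study Design and objective 2 both speak of recovery in people without appendectomy. Nothing readable says that controls go without preparation. On this view the control inclusion list has simply lost a line. Since the sentence opens with a reference back to the people just described, the first exclusion list could even be read as covering the controls too. The technical route announced under Study Process is a figure not available here, and it may show the control pathway.

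Much of this stands. If that sentence governs recruitment, PEG exposure does not confound the comparison. A reader might infer from the control lists that controls are not scoped and that objective 2 therefore cannot be answered. The documents do not support that: the lists are silent on colonoscopy for controls and do not rule it out, and complete confounding needs every control to be unprepared. A reader might also infer that controls are enrolled without any screen for colonoscopy contraindications. That goes too far as well, because the only contraindication named is excluded in both groups.

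What the reply does not remove is the contradiction itself. Both control lists are silent on colonoscopy and PEG, and the only sentence to the contrary sits inside the other group's exclusions. The figure could clarify intent but would not bring the lists into agreement. The conflict with objective 2 is an inference, because its normal population is not defined, but recovery has little meaning without the exposure.

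**Conclusion.** The point holds as an internal contradiction in the definition of the controls, with a conditional risk of confounding. The wording mismatch is certain. The control criteria permit people who never receive PEG, and PEG intolerance is excluded in one group only.

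The harm depends on who is enrolled. The bias in the between-group difference in change is the unprepared fraction of controls times the PEG effect: all of the PEG effect if no control is prepared, part of it if some are, none if all are. The f × P result does not depend on the size of P. The 5 and 5 split and the PEG effects of 0.5 to 2 SD are illustrative assumptions, and the rejection probabilities apply only to the extreme case of no prepared controls. In a study of about 10 people, even one or two unprepared controls would be a sizeable fraction of the group, so the lists should be reconciled before recruitment.

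**What to change.** Reconcile the inclusion and exclusion sections so that they give one definition of the controls:

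1. Add to the control inclusion list that controls are people without appendectomy who are already scheduled for colonoscopy with PEG preparation and who give samples at the same time points as the appendectomy group.
2. Move the sentence that defines the controls out of the first exclusion list and into the control inclusion criteria.
3. Align the two exclusion lists, including PEG intolerance and the wording on contraindications.

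This follows the Protocol's own statement of who the controls are and changes nobody's care, because it selects people already having the procedure. If unprepared controls were in fact intended, the Protocol should say so and restate objective 2, since the contrast would then no longer isolate the appendix.

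The cost is a change of wording and a slightly narrower pool of eligible controls. The change removes confounding by PEG exposure; it does not make the groups alike in other respects.
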